The primary objective of this pilot study is to assess the effects and the effectiveness, both post-treatment and at 1- and 3-month follow-ups, of a group intervention inspired by the principles of Well-Being Therapy (WBT), combined with a nutritional education, compared to treatment as usual (TAU), namely a Basic Nutritional Intervention (BNI) in a group setting, in terms of weight loss (primary outcome).

Date: 21/11/2023 Version number: 4.0

The secondary objective is to evaluate the effects and effectiveness of this intervention, both post-

treatment and at 1- and 3-month follow-ups, compared to BNI, in promoting healthy and sustainable

eating behaviors (in terms food choices, cooking, food storing, consumption and disposal) and an

optimal psychological functioning. This includes the promotion of balanced psychological well-being

levels and functional eating styles, and the reduction of both psychological distress and dysfunctional

cognitive justification mechanisms use (secondary outcomes).

HYPOTHESES

Regarding the first objective, it is hypothesized that the psychological intervention inspired by the

principles of WBT, compared to BNI, will lead to a greater reduction in body weight, both post-

intervention and at 1- and 3-month follow-ups.

Concerning the second objective, it is hypothesized that this intervention, compared to BNI, will be

more effective in promoting healthy and sustainable eating behaviors (in terms food choices, cooking,

food storing, consumption and disposal) and an optimal psychological functioning. This includes the

promotion of balanced levels of psychological well-being and of functional eating styles, and a reduction

of psychological distress and dysfunctional cognitive justification mechanisms use.

METHODS

Study Design

This study, conducted in six phases, is a randomized, controlled, monocentric longitudinal pilot study.

Phase 1. In the initial phase, participants will be recruited from patients with obesity treated in the

Clinical Nutrition and Metabolism Unit of Sant'Orsola Hospital in Bologna and who are selected for the

participation in a Basic Nutritional Intervention (BNI) course. After an initial screening assessment

conducted by a researcher under the supervision of the Unit's referring physician, eligible patients

interested in participating in the study will be asked to provide their informed consent for study

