Phases 5 and 6. These phases will involve assessments of anthropometric variables (weight, height), lifestyle variables (e.g., physical activity, alcohol consumption, smoking, etc.), and psychological variables of interest in both the experimental and control groups at 1- and 3-month follow-ups.

OUTCOMES

All outcomes will be assessed at baseline (T0), post-intervention (T1), and at 1 (T2) and 3 months (T3) follow-ups.

Date: 21/11/2023 Version number: 4.0

Primary Outcome:

• Weight loss, measured in kilograms and expressed in percentage of weight loss in both the experimental and control groups, assessed in terms of change over time and in reference to the intervention condition. A reduction of at least 3% compared to the baseline assessment is expected at T1, with a maintenance of this weight loss at T2 and T3 and with a higher incidence of weight loss in the experimental group compared to the control group. The choice of this criterion has been based on retrospective audits conducted in the same Hospital Unit.

Secondary Outcomes:

- Increase in healthy and sustainable dietary behaviors measured through the Sustainable and Healthy Dietary Behaviors Scale (SHDB; Kawasaki et al., 2022).
- Balancing of psychological well-being levels measured through the Psychological Well-Being Scales-42 (PWBs; Ryff & Keys, 1995; Ruini et al., 2003).
- Promotion of functional eating styles assessed through the Dutch Eating Behavior Questionnaire (DEBQ; Van Strien et al., 1986; Dakanalis et al., 2013).
- Reduction of psychological distress levels measured through the Depression and Anxiety Stress Scale-21 (DASS-21; Lovibond & Lovibond, 1995; Bottesi et al., 2015).
- Reduction in the use of dysfunctional cognitive justifying mechanisms related to food intake evaluated through an adapted assessment index from Plazonic & Herrada (2020).

Participants

Inclusion Criteria. Patients will be eligible for inclusion in the study if they: a) are affiliated with the Clinical Nutrition and Metabolism Unit of Policlinico S. Orsola-Malpighi; b) have a BMI \geq 30; c) are aged \geq 18 years; d) voluntarily agree to participate in the study; e) have access to a computer and can use it independently.

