Phases 4, 5, and 6 – Post-intervention and Follow-up Assessments

At the end of the intervention and at the 1 and 3-month follow-ups, all participants will fill-in the following questionnaires online:

- Ad-hoc form for anthropometric data evaluation for assessing Body Mass Index (BMI) and changes in lifestyle (e.g., physical activity, alcohol consumption, smoking).
- Sustainable and Healthy Dietary Behaviors (SHDB; Kawasaki et al., 2022).
- Psychological Well Being Scales 42 item (PWB; Ryff, 1989; Ruini et al., 2003).
- Dutch Eating Behavior Questionnaire (DEBQ; Van Strien et al., 1986; Dakanalis et al., 2013).
- Depression and Anxiety Stress Scale-21 (DASS-21; Lovibond & Lovibond, 1995; Bottesi et al., 2015).
- Assessment of Justificatory Cognitive Mechanisms (adapted from Taylor & Sheeran, 2014; Plazonic & Herrada, 2020).

Body weight assessment will also be verified by the medical staff during follow-up visits.

CONTEXT

The study will be conducted partly at Policlinico Sant'Orsola-Malpighi, in the Clinical Nutrition and Metabolism Unit of S. Orsola Hospital, and partly online via the Microsoft Teams platform.

Date: 21/11/2023 Version number: 4.0

STATISTICAL CONSIDERATIONS

Sample Size Calculation

The sample size was assessed using G*Power 3.1 statistical software. Based on a previous study conducted in the same recruitment center with the same clinical population (Zhu et al., 2022), the sample size was estimated considering an effect size of 0.25, a type I error < 0.05, and a type II error (power) of 0.95, for 2 groups and 4 measurements (baseline; post-intervention; 1-month follow-up; 3-month follow-up). It is estimated that a sample size of 36 subjects is sufficient. Considering a 30% dropout risk in this clinical population (Brantley et al., 2014), it is estimated to recruit approximately 50 subjects, 25 for the experimental condition and 25 for the control condition.

Statistical Analysis

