Statistical Package for Social Science 29.0 (SPSS) will be used for data analysis. Descriptive statistical analyses (frequencies, means, medians, modes, and standard deviations) will be conducted to analyze the sociodemographic, anthropometric, clinical characteristics, and lifestyle of the sample, as well as the mean scores on administered questionnaires. To assess differences between the experimental and control groups at post-intervention and the 1- and 3-month follow-ups in terms of weight loss, healthy and sustainable dietary behaviors, and optimal psychological functioning (psychological well-being, eating styles, psychological distress, and use of justification mechanisms), repeated measures analysis of variance (ANOVA) will be performed, using time (T0, T1, T2, T3) as a within-subject factor and group (E or C) as a between-subjects factor. Missing data will be handled through Intention to Treat (ITT) Analysis. Differences will be considered significant at $p \le 0.05$.

ETHICAL PROCEDURES

The procedures regarding the conduction, execution, and data collection of this research adhere to the ethical principles outlined in the Declaration of Helsinki and its revisions. The study will be conducted in accordance with regulatory requirements and legal obligations (DM 17/12/2004).

During the screening phase, eligible subjects will receive all relevant information on the study, both in written and oral form. Additionally, before proceeding with data collection, informed consent and consent for the processing of personal data will be obtained for each participant, in an anonymous and aggregated form, in accordance with Law 675/1996 and Law 196/03 on the protection of individuals and the processing of personal data.

A copy of the informational and consent forms for participation in the research and data processing will be presented by the referring physician to the potential participant deemed eligible for the study. If interested, the participant will sign the consent forms, which will be collected and stored in a designated

Date: 21/11/2023 Version number: 4.0

space at the Department while informational forms will be left to the participant.

The data collected will be digitized anonymously using statistical software for data processing (SPSS).

Furthermore, a decoding list of the code assigned to each individual participant will be securely stored

in encrypted form exclusively at the Department of Psychology of the University of Bologna.

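### The planned time-by-group ANOVA cannot show greater weight loss at T1, T2 and T3: no between-arm estimate or CI is planned at any visit, and no sphericity correction is stated

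*Combined protocol and SAP*

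**What the plan says.** The Hypotheses section states that the experimental intervention, compared with the Basic Nutritional Intervention (BNI), "will lead to a greater reduction in body weight" at post-intervention and at the 1- and 3-month follow-ups. The Primary Outcome entry gives weight loss in kilograms and as a percentage, "assessed in terms of change over time and in reference to the intervention condition". It adds an expectation, "A reduction of at least 3% compared to the baseline assessment is expected at T1", kept at T2 and T3, "with a higher incidence of weight loss in the experimental group compared to the control group".

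The Statistical Analysis section gives its purpose as "To assess differences between the experimental and control groups at post-intervention and the 1- and 3-month follow-ups in terms of weight loss" and other outcomes. It then names one inferential method for all of them: "repeated measures analysis of variance (ANOVA) will be performed, using time (T0, T1, T2, T3) as a within-subject factor", with group between subjects and significance at p ≤ 0.05. It does not say which ANOVA term decides. It plans no visit-wise contrast, no between-arm estimate, no confidence interval and no sphericity correction. The descriptive statistics, including means and SDs, are planned for the sample and not explicitly by arm.

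Under Sample Size Calculation, with effect size 0.25, alpha 0.05, power 0.95, two groups and four measurements: "It is estimated that a sample size of 36 subjects is sufficient".

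**The concern.** The hypothesis has a direction (more loss), three time points, and implicitly a claim about maintenance. An omnibus group-by-time F has none of these. It asks only whether the two arms' profiles over T0-T3 are parallel. A significant result is compatible with a benefit that lasts, a benefit that disappears, or harm. If the plan is followed as written, the primary test can be positive while the stated hypothesis is still undecided. The visit-wise comparisons would then be chosen after the data are seen.

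The F also assumes sphericity, that is, equal variances for all pairwise differences between visits. Weight measured over several months may well not meet this. Without a stated rule, the plan does not say whether the uncorrected or the corrected result decides significance.

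**Working it through.** **1. Which term decides.** Inputs from Sample Size Calculation: f = 0.25, alpha 0.05, k = 2 groups, m = 4 measurements. Correlation ρ = 0.5 and epsilon = 1 are assumed, because neither is stated.

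Interaction: λ = f²·N·m/(1−ρ), with df (k−1)(m−1) and (N−k)(m−1).
- N = 36: λ = 0.0625 × 36 × 4 / 0.5 = 18; df 3 and 102; power 0.952.
- N = 34: λ = 17; df 3 and 96; power 0.939.

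So 36 is reproduced. A between-group main effect, with λ = f²·N·m/(1+(m−1)ρ), would need N = 132. The trial is therefore sized on group-by-time.

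**2. What that F can show.** For between-arm differences d at T0-T3, in SD units, f² is the mean over the four visits of ((d − mean d)/2)². Each pattern below has squared deviations summing to 1.0, so f² = 1.0/(4 × 4) = 0.0625 and f = 0.25, and power at N = 36 is 0.952 for every one:
- experimental arm better throughout: 0, −1.155, −1.155, −1.155
- worse throughout: 0, 1.155, 1.155, 1.155
- better at T1 only: 0, −1.155, 0, 0
- better at T3 only: 0, 0, 0, −1.155
- better at T1, worse at T3: 0, −0.707, 0, 0.707

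**3. Size under assumed weight data.** The documents give no SDs or correlations, so a range is shown. Simulation used 20,000 runs per setting and 18 per arm (36/2), on percentage change. GG is Greenhouse-Geisser. Sustained means a 2.5-point benefit at all visits; fading means 2.5/1.25/0 points.

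| SD at T1/T2/T3, adjacent-visit correlation | Type I, uncorrected | Type I, GG | GG significant: sustained | GG significant: fading | All three CIs favour experimental arm: sustained |
|---|---|---|---|---|---|
| 2/3/4, 0.85 | 0.081 | 0.049 | 0.60 | 0.68 | 0.41 |
| 2.5/3/4, 0.85 | 0.077 | 0.051 | 0.61 | 0.67 | 0.42 |
| 3/3/3, 0.8 | 0.062 | 0.047 | 0.71 | 0.73 | 0.49 |
| 2/3.5/5, 0.9 | 0.093 | 0.049 | 0.39 | 0.38 | 0.29 |
| 3/3/3, 0.5 | 0.053 | 0.044 | 0.66 | 0.57 | 0.40 |

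A sustained 2.5-point harm is significant in 39-71% of runs, essentially as often as the same-sized benefit.

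**4. Why type I error rises.** Take equal SD s for each change from baseline. If all changes correlate at 0.5, the variance between two post-baseline visits is 2s²(1 − 0.5) = s². That equals the variance of each change from T0, so sphericity holds; the simulated uncorrected rate is 4.9%. If the changes are uncorrelated, the first variance is 2s² against s², and the rate is about 6%. The driver is unequal variances of the pairwise differences, not correlation as such.

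**5. Precision of visit-wise differences.** The unadjusted 95% half-width is t(0.975, 2n−2)·√(2/n) SDs: 0.68 at n = 18 and 0.57 at n = 25, about 16% narrower (0.57/0.68 = 0.84). At n = 18 the simulated baseline-adjusted half-widths are ±1.4 to 2.1 points at T1, 2.1 to 2.4 at T2 and 2.1 to 3.4 at T3.

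**The case against.** The strongest reply is that the plan does state the visit-wise aim, "To assess differences between the experimental and control groups at post-intervention and the 1- and 3-month follow-ups", and that arm means would be read beside the F. A reader might infer that direction would be wholly invisible. The documents do not support that: the outcome is to be expressed in both arms, so means would show direction descriptively. What remains is that no between-arm estimate or interval is planned to carry the claim.

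A second reply is that a single-visit or T1-T3 average contrast would be no better. That is fair. A T1 contrast has the same power for both scenarios above, and an average does not test maintenance. The average also loses power for a fading effect (0.23 against 0.67 for the corrected interaction, SDs 2.5/3/4). The point is therefore not that one such contrast must be made primary. Requiring all three visit-wise intervals to favour the experimental arm does separate the scenarios: if the true T3 difference is zero, the T3 interval favours that arm in at most 2.5% of trials.

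Third, the type I inflation is modest in most settings, and 9% is the extreme of an assumed range. That stands.

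Fourth, a reader might infer that the 3% criterion is a primary responder endpoint left without a test. The text words it as an expectation drawn from local audits, and no responder endpoint is defined. A by-arm count would be useful but is minor. So is the unstated choice of kilograms or percentage: with the correction, counting either scale as significant gives 5.1-5.9% under the null.

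Finally, this is a pilot. It nevertheless states directional hypotheses, 95% power and a significance threshold, and a pilot has particular use for estimates with intervals.

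**Conclusion.** The concern holds, and the plan should be changed before analysis. The main part needs no numerical assumption: a 3-df group-by-time F carries no direction, visit or maintenance, while the hypothesis requires all three. That this is the deciding term is an inference. The Statistical Analysis section does not name it, but the stated 36 reproduces for it (power 0.952, with ρ = 0.5 and epsilon = 1 assumed) and not for a group main effect.

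The sphericity part is secondary and rests on assumed SDs and correlations. Uncorrected type I error is about 5-6% with equal SDs, 7.7% in an intermediate setting, and 8-9% when the SD of change at least doubles from T1 to T3. With Greenhouse-Geisser it is 4.4-5.1%.

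A reader might go further and infer that the ANOVA is invalid or that the trial cannot answer its question. Neither follows. The F is a legitimate test of non-parallel profiles, and the data needed for the visit-wise comparisons are already scheduled for collection.

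**What to change.** 1. Pre-specify the between-arm difference in percentage weight change, adjusted for baseline weight, with 95% CI at each of T1, T2 and T3. Claim the hypothesis in full only if all three intervals favour the experimental arm. That joint claim needs no multiplicity adjustment. If the three do not all favour it, treat the intervals as estimates and make no visit-specific claim of significance.
2. If the ANOVA is kept, name group-by-time as its deciding term and use the Greenhouse-Geisser result.
3. Optional and minor: tabulate loss of at least 3% by arm, labelled supportive.

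The cost is a few sentences of text and a little more analysis, with no new data. The drawbacks should be stated openly. The intervals are wide at 18 per arm and only about 16% narrower if all 25 per arm contribute. Joint power at all three visits is about 0.3-0.5 for a sustained 2.5-point benefit at 18 per arm, below the 0.39-0.71 of the corrected F. That is the price of a rule that matches the stated hypothesis.

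### Baseline (T0) is analysed as a fourth response level with no baseline covariate, which costs precision on the continuous questionnaire scores and leaves chance T0 imbalance in the group contrast

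*Combined protocol and SAP*

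**What the plan says.** The aim of the analysis is given as "To assess differences between the experimental and control groups at post-intervention and the 1- and 3-month follow-ups". The outcomes covered are weight loss, healthy and sustainable dietary behaviours, and "optimal psychological functioning (psychological well-being, eating styles, psychological distress, and use of justification mechanisms". One model serves all of them: "repeated measures analysis of variance (ANOVA) will be performed, using time (T0, T1, T2, T3) as a within-subject factor". Its only other term is "group (E or C) as a between-subjects factor". The section names no covariate and does not say whether the test is group x time, the group main effect or a set of per-visit contrasts.

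The Sample Size Calculation uses the same structure, "for 2 groups and 4 measurements (baseline; post-intervention; 1-month follow-up; 3-month follow-up", so baseline counts as one of the four measurements. The Outcomes section confirms that the covariate would be available: "All outcomes will be assessed at baseline (T0), post-intervention (T1), and at 1 (T2) and 3 months (T3) follow-ups". Study Design, Phase 2, describes 1:1 block randomisation and mentions no stratification by any baseline score.

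**The concern.** The question concerns group differences after treatment, but the model treats the pre-treatment score as one more response. Without a constraint that the arms share a T0 mean, the group effect is read in one of two ways. The first is a difference in change from T0, which subtracts the whole baseline score when only part of it predicts follow-up. The second is the group main effect, which averages in a visit where no treatment effect can exist, so an effect constant over T1-T3 shrinks to 3/4 of its size.

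Precision matters with about 50 patients recruited and 36 needed for analysis. Five secondary domains rest on self-report, and a chance T0 difference in distress or well-being could mimic or mask part of a treatment effect. Adjusting for T0 uses data already planned.

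**Working it through.** **Inputs from the documents.** "effect size of 0.25, a type I error < 0.05, and a type II error (power) of 0.95"; 2 groups and 4 measurements; "It is estimated that a sample size of 36 subjects is sufficient"; about 50 recruited, 25 per arm.

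**Assumptions.** The documents give no between-visit correlation (rho) and no SDs. I assume equal SDs and equal correlations between visits, and show a range of rho. Effects are in SD units.

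**Reproducing the plan's N.** I read 0.25 as Cohen's f and use the G*Power within-between interaction formula with rho 0.5 and sphericity: lambda = N x m x f² / (1 - rho) = 36 x 4 x 0.0625 / 0.5 = 18, with df 3 and 3 x 34 = 102. Power is 0.952, which matches N = 36. The between-factor formula at rho 0.5 would need 132. The plan's N therefore fits a time or group x time test.

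**Variance at one visit** (common multiplier 2/n per arm omitted).
- Change from T0: 2(1 - rho).
- T0-adjusted: 1 - rho².
- Ratio: (1 + rho)/2. Estimating the slope costs a factor 1 + 1/(N - 4) = 33/32 = 1.031 at N = 36.

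**Variance for the mean of T1-T3.**
- Change: (1 + 2rho)/3 + 1 - 2rho.
- T0-adjusted: (1 + 2rho)/3 - rho², with the same factor 1.031.

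| rho | One visit: change v adjusted | Ratio | Ratio with cost | T1-T3 mean: change v adjusted | Ratio with cost |
|---|---|---|---|---|---|
| 0.5 | 1.00 v 0.75 | 0.75 | 0.77 | 0.667 v 0.417 | 0.64 |
| 0.7 | 0.60 v 0.51 | 0.85 | 0.88 | 0.400 v 0.310 | 0.80 |
| 0.8 | 0.40 v 0.36 | 0.90 | 0.93 | 0.267 v 0.227 | 0.88 |
| 0.95 | 0.100 v 0.0975 | 0.975 | 1.005 | 0.067 v 0.064 | 0.99 |
| 0.98 | 0.040 v 0.0396 | 0.99 | 1.02 | 0.0267 v 0.0263 | 1.02 |

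**Power, 1 df against 1 df**, for a 0.5 SD difference in the T1-T3 mean, 18 completers per arm, two-sided 0.05. At rho 0.5:
- Change: SE = sqrt(0.667 x 2/18) = 0.272, noncentrality 0.5/0.272 = 1.84, 34 df, power 0.43.
- Adjusted: SE = sqrt(0.417 x 2/18 x 1.031) = 0.219, noncentrality 2.29, 33 df, power 0.60.

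The same steps give 0.63 v 0.73 at rho 0.7 and 0.81 v 0.85 at rho 0.8.

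**Chance imbalance.** The T0 difference has SE sqrt(2/25) = 0.283 SD with 25 per arm, so P(|difference| > 0.3 SD) = 0.29. With 18 per arm the SE is 0.333 and the probability 0.37. A change contrast moves by -(1 - rho) per SD of imbalance, so a 0.3 SD imbalance at rho 0.5 shifts it by 0.15 SD in the opposite direction.

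**Simulation check** (4,000 trials per setting, 36 patients). At rho 0.5 with no effect, the SD of the T1-T3 estimate was 0.27 for change and 0.22 for adjusted. Its correlation with T0 imbalance was -0.61 for change, +0.79 for the group main effect and 0.00 for adjusted. Type I error was 0.043 for the planned interaction test and 0.047 for the adjusted test.

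**The case against.** The strongest reply is that the planned ANOVA is a recognised, valid method in a pilot trial. That stands. A reader might infer from T0 sitting among the responses that the analysis is biased or has an inflated error rate. Neither follows: over repeated randomisations the change contrast is unbiased, simulated type I error is close to 5%, and ordinary chance imbalance is already in its standard error. The loss is of efficiency, plus an avoidable shift in any trial that happens to be imbalanced.

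Four further limits stand.
- **Primary outcome.** A reader might expect adjustment to help every outcome. For body weight, with rho about 0.95 or more (an assumption), the cost of estimating the slope cancels the gain.
- **Size.** Rho 0.5 reproduces N = 36, but that is a back-solved design input and says nothing about how these questionnaires behave. At rho 0.8 the gain is modest.
- **Power.** The figures compare two 1-df contrasts. They are not the power of the plan's own test, which the plan does not name and whose sample size fits a multi-df test.
- **Scope.** The justification index partly records which of six mechanism types a patient chooses. That part is nominal, and these formulas do not cover it.

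Keeping T0 as a response is not wasteful in itself: a longitudinal model that constrains the arms to a common T0 mean performs like covariate adjustment. The plan specifies no such constraint.

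The timing of T0 is also unclear. Study Design puts allocation in Phase 2 and the first questionnaire in Phase 3, while Methods of Assessment labels the baseline assessment Phase 2. If patients know their arm when they answer, a T0 difference need not be chance, and adjustment loses its premise.

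**Conclusion.** The point holds as a precision improvement worth making, not as an error that invalidates the analysis. Under equal SDs and correlations and 36 completers, T0 adjustment lowers single-visit variance for the continuous questionnaire scores by about 23%, 12% or 7% at rho 0.5, 0.7 or 0.8. For the T1-T3 mean the reductions are about 36%, 20% and 12%. It also removes the chance-imbalance component, provided T0 is truly pre-randomisation. For body weight the effect is neutral, within about 2% either way. The size depends on a correlation that the documents do not give.

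**What to change.** 1. For each continuous outcome, fit T1, T2 and T3 as the repeated levels, with group, time, group x time and the centred T0 score of the same outcome as covariate. Use SPSS MIXED rather than GLM repeated measures, so that patients missing a visit are kept; the plan expects 30% dropout. A longitudinal model constraining the arms to a common T0 mean is an equivalent choice.
2. Name the T0-adjusted group difference averaged over T1-T3 as the test, and report per-visit differences. This is needed because group x time over T1-T3 no longer captures a sustained effect.
3. For weight, analyse loss at T1-T3 with T0 weight as covariate.
4. Specify a separate analysis for the nominal part of the justification index.
5. Reconcile Study Design with Methods of Assessment on whether T0 is completed before allocation is known.
6. Note in the Sample Size Calculation that N = 36 was computed for the four-level ANOVA, and state the correlation assumed.

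The cost is one error degree of freedom and a few sentences of text. No new data, visits or patients are needed.

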Weight measurement will also be confirmed by the Unit's referring physician during routine patient visits. Participants in the experimental group will participate in 6 weekly group session of two hours each. One part will be held by a trained dietitian and will focus on nutritional education, particularly emphasizing the adoption of healthy and sustainable eating behaviors. Nutritional education will cover topics related to the causes and risk factors of obesity, nutritional principles of foods, preparation of balanced meals, food labels reading, and the importance of physical activity. The remaining part will be dedicated to a group psychological intervention inspired by the principles of Well-Being Therapy (WBT; Fava, 2016a) and will be held by a trained psychologist. This intervention aims to promote weight loss, healthier and more sustainable eating behaviors, and an optimal psychological functioning. During these sessions, participants will be introduced to the six dimensions of psychological well-being: 1) selfacceptance, 2) personal growth, 3) purpose in life, 4) positive relations with others, 5) environmental mastery, and 6) autonomy (Ryff, 1996). Gradually, cognitive-behavioral strategies will be provided to enhance psychological well-being and seek a balance between the presented dimensions through selfmonitoring of well-being episodes, restructuring thoughts that interrupt well-being, and exposure tasks to optimal experiences. Additionally, participants will be given cognitive-behavioral tools to recognize justifying cognitive mechanisms and replace them with more functional cognitions related to eating. These objectives will also be achieved through the use of a food diary to highlight emotions and thoughts experienced during food intake. The control group, on the other hand, will receive treatment as usual (TAU) by participating in 6 two-hour group sessions of Basic Nutritional Intervention (BNI) held by a trained dietitian. This course focuses on promoting healthier lifestyles through nutritional education, diet monitoring using a dedicated food diary, and recommendations for proper physical activity.

Phase 4. A post-intervention assessment will be conducted for anthropometric variables (weight, height), lifestyle variables (e.g., physical activity, alcohol consumption, smoking, etc.), and psychological variables of interest in both the experimental and control groups.

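### Intention to treat is named as the missing-data method, but it neither fills nor models missed visits; run as written, the four-visit repeated-measures ANOVA becomes a completers analysis

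*Combined protocol and SAP*

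**What the plan says.** The combined protocol and SAP gives one inferential analysis, under Statistical Considerations, Statistical Analysis: "repeated measures analysis of variance (ANOVA) will be performed, using time (T0, T1, T2, T3) as a within-subject factor", with arm as the between-subjects factor, in SPSS 29.0. It covers weight loss and all the secondary outcomes. The one sentence on missing data is "Missing data will be handled through Intention to Treat (ITT) Analysis". The document does not define the ITT set. It gives no imputation or carry-forward rule, no likelihood-based model, no assumption about why data are missing, and no sensitivity analysis.

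Missing data are expected. The Sample Size Calculation section raises 36 to about 50 with the words "Considering a 30% dropout risk in this clinical population". It does not say when dropout occurs or whether it means missing outcome data.

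Weight has a second source. Under Study Design, "Weight measurement will also be confirmed by the Unit's referring physician during routine patient visits"; under Methods of Assessment, for the later visits, "Body weight assessment will also be verified by the medical staff during follow-up visits". Neither place says that the staff value is used when the participant's form is missing. For the questionnaires, "all participants will fill-in the following questionnaires online".

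The primary outcome carries a criterion at one visit: "A reduction of at least 3% compared to the baseline assessment is expected at T1, with a maintenance of this weight loss at T2", continuing to T3, with a "higher incidence of weight loss in the experimental group compared to the control group".

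**The concern.** ITT and a missing-data method answer different questions. ITT fixes the analysis population and the arm in which each person counts. It does not say what to do when a person in that population has no weight at T2 or T3. A conventional repeated-measures ANOVA needs all four values per person and deletes incomplete cases. The two sentences can therefore both be carried out only with a step the plan does not state. Without it, the analysed set is no longer everyone randomised.

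Two things are at stake. First, people who stay may differ from people who leave. If poor losers leave, each arm's mean loss is overstated, and the arm contrast is biased if that dependence differs between arms. Second, collected data are lost: someone who attends T0, T1 and T2 but misses T3 is removed from every comparison, including the T1 comparison where the 3% criterion is set.

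The choice is also open. One analyst might run completers, another carry values forward, another impute, and each could claim to follow the section. Their primary results could differ.

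**Working it through.** **1. The plan's own sample size.** Stated inputs (Sample Size Calculation): effect size 0.25, alpha 0.05, power 0.95, 2 groups, 4 measurements. Assumed because not stated: the effect size is Cohen's f, the correlation between measurements is 0.5, and sphericity holds. For the group-by-time test:

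- noncentrality = f² x N x m / (1 - correlation) = 0.0625 x 36 x 4 / 0.5 = 18.0
- degrees of freedom = 3 and (36 - 2) x 3 = 102
- power = 0.952; at N = 34 it is 0.939, so 36 is the smallest even total that reaches 0.95

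This reproduces the stated 36. For dropout, 36 / 0.70 = 51.4, consistent with the stated target of about 50.

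**2. How many remain if incomplete cases are deleted.** 50 x (1 - 0.30) = 35, if the 30% means at least one missing outcome. At 10%, 20% and 40% the count would be 45, 40 and 30.

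**3. Does this cost power against the plan?** At N = 35 the noncentrality is 0.0625 x 35 x 4 / 0.5 = 17.5, with 3 and 99 degrees of freedom, and power is 0.946. The difference from 36 is 0.952 - 0.946 = 0.006. The target of 50 was set to leave about this many people.

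**4. How far could completers mislead? Illustration only.** The documents give no SD and no dropout mechanism, so these inputs are assumed: 30% leave after T1; the odds of leaving rise by a factor of 1.35 to 2.72 for each SD of poorer T1 loss (logistic); percentage loss at T1 is normal with SD 3.0 points. Averaging T1 loss over those who stay gives an upward shift of 0.088 SD at odds ratio 1.35 and 0.253 SD at 2.72. In points:

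| Odds ratio per SD | Shift in SD | Overstated mean T1 loss |
|---|---|---|
| 1.35 | 0.088 | 0.088 x 3.0 = 0.27 |
| 2.72 | 0.253 | 0.253 x 3.0 = 0.76 |

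(Products are taken from unrounded shifts.) A true mean loss of 3.0% at T1 would then read 3.27% to 3.76%, although the T1 weights of the later dropouts had been collected.

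**5. The arm contrast.** With no true difference and the same dependence in both arms, the shifts cancel: 0.76 - 0.76 = 0. If one arm followed odds ratio 2.72 and the other 1.35, the T1 contrast would be off by 0.76 - 0.27 = 0.49 points; if dropout in the other arm were random, by 0.76. The contrast is therefore at risk only when the dependence differs by arm.

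**The case against.** The strongest reply is that this is an unstated detail, not a wrong choice. The ITT sentence most naturally signals an intention to keep everyone randomised, so some fill-in step was presumably meant, and the figures in step 4 describe a branch that the sentence disclaims. That is fair as far as it goes: the documents do not support a claim that the plan has chosen a completers analysis. But no fill-in step is written anywhere, and the analysis that is written deletes incomplete cases.

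A second reply is that dropout is already in the sample size. This stands for power. A reader might infer from 35 of 50 that the trial loses its planned power; step 3 shows that it does not. Lower values can be produced by assuming a weaker correlation or non-sphericity, but those apply almost equally at the planned 36 and are not a consequence of missing data. Allowing for dropout in the numbers does not protect against bias.

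A third reply is that staff check weight, so a missed online form need not mean a missing primary outcome. This also stands in part, and is why the 35 is conditional. But the plan does not say that the staff value is substituted, or that it is obtained for people who stop attending. For the questionnaires only online completion is described; Ethical Procedures mentions paper as well as digital data, but no paper route for these forms.

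Finally, a reader might infer that the trial will show a false advantage for one arm. Nothing in the documents says that dropout depends on weight loss, or does so differently by arm.

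The study is called a pilot, which limits the weight of the point. Even so, its primary objective is effectiveness on weight loss and it sets a significance threshold.

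**Conclusion.** The point holds and should be fixed before the data are analysed. The named method does not deal with missing data, and the named analysis, run as written, would drop everyone with an incomplete record: 15 of 50 if the planned 30% means missing outcomes. This departs from the stated ITT intent and throws away T1 and T2 data already in hand.

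The size of any bias is unknown. The 0.27 to 0.76 points at T1 rest entirely on assumed values for the SD and the dropout mechanism, and apply only if nothing is filled. They show that the effect need not be trivial beside a 3% criterion; they are not estimates for this trial. Loss of power is not part of the conclusion.

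**What to change.** Replace the ANOVA and the ITT sentence with a linear mixed model for repeated measures: SPSS MIXED, REML, unstructured covariance, a small-sample degrees-of-freedom method, with arm, visit and arm-by-visit terms. Fit it to all randomised participants in their assigned arm, using all available visits, for weight and for the secondary outcomes that are scale scores. State the missing-at-random assumption. Percentage loss is zero for everyone at T0, so either model it at T1 to T3 with baseline weight as a covariate (people with no later weight then contribute nothing) or model weight itself at T0 to T3; a log scale is optional.

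Multiple imputation before the planned ANOVA is an acceptable alternative if the imputation model and the pooling are stated.

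In addition:

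- State that the staff-verified weight is used when the online form is missed.
- Report the 3% result at T1 from all available T1 weights. If it is reported as a proportion, say how a missing T1 weight counts.
- Add one sensitivity analysis for data not missing at random, for example missing weights shifted toward baseline by stated amounts.

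A complete-case ANOVA may be kept as supportive; it is not needed.

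The cost is SAP wording and another procedure in the same software, with no new patients or data. The limitation is that missing at random cannot be checked from the data. If people leave because of weight change that was never recorded, the mixed model does not remove the bias, which is why the sensitivity analysis is needed.
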